### 8.3.1 Patient-Reported Outcomes

Patient-Reported Outcomes (PRO) analyses will use data from the FAS. PRO will be assessed at Cycle 1 Day 1, at all study treatment day 1 of each cycle, and at Safety Follow up visit, following the European Organisation for Research and Treatment of Cancer (EORTC) Quality-of-Life Questionnaire Core 30 (QLQ-C30) tool (Aaronson, 1993).

Fifteen separate scales/items within 3 broad categories (9 multi-item scales and 6 single-item symptom measures) will be assessed (Fayers, 2001):

- Global health status / QoL (revised) (Items 29 and 30)
- Functional scales
  - Physical functioning (revised) (Items 1 to 5)
  - Role functioning (revised) (Items 6 and 7)
  - Emotional functioning (Items 21 to 24)
  - Cognitive functioning (Items 20 and 25)
  - Social functioning (Item 26 and 27)
- Symptom scales
  - Fatigue (Items 10, 12 and 18)
  - Nausea and vomiting (Items 14 and 15)
  - Pain (Items 9 and 19)
  - Dyspnea (Item 8)
  - Insomnia (Item 11)
  - Appetite loss (Item 13)
  - Constipation (Item 16)
  - Diarrhea (Item 17)
  - Financial difficulties (Item 28)

The EORTC QLQ-C30 will be scored according to its user guides (<https://www.eortc.org/app/uploads/sites/2/2018/02/SCmanual.pdf>) (Fayers, 2001).

Pfizer Inc. / Protocol: TTI-621-03/C4961003  
IQVIA Biotech (Confidential) Project # YXA42460

*Time to first worsening of PRO assessments* is defined as the time from the first PF-07901800 infusion (Cycle 1 Day 1) to the first observation of at least a 10-point decrease from baseline in the standardized score (linear transformation) of Global Health Status/QoL (Osoba, 1998). Patients without a worsening event will be censored on the last date of PRO assessments or the date of first study treatment, whichever is the latter. The number of events and the number of censored patients will be summarized only for expansion cohorts. The median time to event (reported in days), its 95% confidence interval, and the 25th and 75th percentiles on the time to event will be summarized using Brookmeyer-Crowley method.

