## 6.3 Definition of Baseline

Baseline is defined as the last measurement taken prior to the first infusion of study medication (Cycle 1 Day 1).

The average of the pre-infusion results will be considered as the baseline value for vital signs taken at different timepoints on the same pre-infusion day.

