## 6.5 Missing Data

Due to the study design, data will be reported as collected and no imputation methods of missing values will be performed, except for partial dates. Below it is addressed how missing information will be handled for partial dates and incomplete disease assessments.

When no imaging/measurement is done at all at a particular time point, the patient is not evaluable (NE) at that time point. If only a subset of lesion measurements are made at an assessment, usually the case is also considered NE at that time point, unless a convincing argument can be made that the contribution of the individual missing lesion(s) would not

Pfizer Inc. / Protocol: TTI-621-03/C4961003  
IQVIA Biotech (Confidential) Project # YXA42460

change the assigned time point response, which is most likely to occur in the case of PD (e.g., if only 2 of 3 baseline target lesions are assessed and result in a > 20% increase in the sum, then the patient would be assessed as a PD regardless of the missing lesion).

Partial dates are allowed on the eCRF for prior disease therapy start and stop dates, adverse event (AE) onset and end dates, concomitant medication start and stop dates, and concomitant procedure, procedure dates. An entry for the year is required in the eCRF system for each of these dates. Only the month and day may be entered as unknown. Dates from these forms will be reported in listings as collected. Every effort will be made to query missing dates.

For records with missing AE onset date, the following procedure will be employed for use in determining whether the AE is treatment emergent:

- AE onset dates with missing day and non-missing month will be assumed to occur on the first day of the non-missing month, except for AEs occurring in the month and year of first dosing, in which case the date will be imputed using the date of first dosing.
- AE onset dates with missing day and month will be assumed to occur on the first day of the non-missing year (*i.e.*, January 1), except for AEs occurring in the year of first dosing, in which case the date will be imputed using the date of the first dosing.
- AEs that are not ongoing and have an end date with missing day and non-missing month, they will be assumed to occur on the last day of the month, except when the end of study date or date of death is prior to the last day of the month. The date will be imputed as end of study date, or death date, whichever happens the earliest.

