## 6.7 Analysis Populations

### 6.7.1 Full Analysis Set (FAS)

The FAS will include patients who were enrolled, allocated to treatment, and received at least one non-zero dose of study treatment.

This analysis population will be used for baseline summaries and the analysis of efficacy endpoints.

Patients will be classified according to the study treatment actually received. For patients who received a wrong study dose, they would be recoded in protocol deviation and dosing compliance; if the wrong dose occurred only once, the analysis will use the patients' initial planned dose as summary cohorts. If more than one wrong dose occurred, the analysis will use patients' actual dose as summary cohorts. If patients' doses were reduced, safety analysis will use the initial planned dose as summary cohorts. Patients receiving different dosing schedules will be presented in the listings only.

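### Time to PRO worsening keeps patients with no baseline score at risk although they cannot have an event; if any occur, the Kaplan-Meier curve can only stay the same or rise

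*SAP*

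**What the plan says.** SAP 8.3.1 sets the population: "Patient-Reported Outcomes (PRO) analyses will use data from the FAS". SAP 6.7.1 defines that set by dosing alone: "The FAS will include patients who were enrolled, allocated to treatment, and received at least one non-zero dose of study treatment". Neither section requires a baseline score.

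The event in SAP 8.3.1 is the "first observation of at least a 10-point decrease from baseline in the standardized score (linear transformation) of Global Health Status/QoL". For everyone else the rule is: "Patients without a worsening event will be censored on the last date of PRO assessments or the date of first study treatment", with the later of the two dates applying. SAP 6.8 refers PRO censoring back to Section 8, so this is the only rule.

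SAP 6.3 takes as baseline the last value before the first infusion. The questionnaire is scheduled on Day 1 of each cycle and at the Safety Follow-Up Visit (SAP 8.3.1; protocol Table 24). It is not on the screening list in protocol Section 11. The pre-dose Cycle 1 Day 1 form is therefore the only possible baseline. Protocol 12.3.4 uses paper forms and says that they should be completed before treatment starts. On missing values, SAP 6.5 states that "no imputation methods of missing values will be performed, except for partial dates".

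The number of events, the number censored, the median with its 95% interval and the quartiles are reported. SAP 8.3.1 limits the event and censoring counts to the expansion cohorts.

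**The concern.** A change from baseline cannot be computed without a baseline. A patient who misses the pre-dose form but completes later ones can never meet the event definition, whatever those later forms show. The censoring rule nevertheless treats this patient as observed and not worsened up to the last form. The patient counts in the denominator at every event time in that period and can never count in a numerator.

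Time to worsening of PRO is a listed secondary endpoint. Cohorts B and C hold 18 and 13 patients (SAP 4.3.2), so one such patient is 1/18 = 6% or 1/13 = 8% of the cohort. At stake is whether the reported median and quartiles describe the patients in whom worsening could be observed.

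**Working it through.** The documents give no median, event count or missing-baseline rate for this endpoint, so there is no figure of the plan to reproduce. The check has three parts.

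**1. Who is affected under the stated rule**

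- No questionnaire at all: censored at first treatment (Day 1). No effect on the curve.
- Baseline form only, completed on Day 1: the last PRO date is the first-treatment date, so also Day 1. No effect.
- No baseline score but later forms: the later date applies, so censored at the last form. No event is possible. This is the affected group.
- Baseline score and later forms, none with a computable global health score: the rule uses the last PRO date, not the last date with a score, so these patients also stay at risk without a possible event. The simulation below does not cover them.

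**2. Direction**

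At event time j let d be the number of events, n the number at risk who have a baseline, and k the number without a baseline who are still returning forms. The Kaplan-Meier factor is 1 − d/(n + k) under the stated rule and 1 − d/n if the k patients are censored at Day 1. Since k ≥ 0, the first factor is never smaller, and neither is the product of the factors. For example, with one event and 2 of 31 patients lacking a baseline, the factors are 1 − 1/31 = 0.968 and 1 − 1/29 = 0.966. The median and quartiles can therefore stay the same or lengthen, but cannot shorten.

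**3. Size under assumptions**

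From the documents: forms on Day 1, every 21 days to Day 127, then every 28 days; cohorts of 31 (planned), 18 and 13. Assumed: true median time to worsening 60, 90 or 120 days; median PRO follow-up 120 to 180 days; independent exponential times; patients without a baseline still return later forms. Each scenario had 2,000 simulated trials. The typical median is the middle value of the Kaplan-Meier medians across trials. On the visit grid, true medians of 60, 90 and 120 days appear at the next visit: Day 64, 106 and 127.

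| Cohort | No baseline | True median (days) | PRO follow-up median (days) | Typical median, stated rule vs Day 1 censoring | Trials with longer median |
|---|---|---|---|---|---|
| 31 | 2 | 60 | 180 | 85 vs 64 | 28% |
| 31 | 2 | 90 | 180 | 106 vs 106 | 34% |
| 31 | 2 | 120 | 180 | 155 vs 127 | 34% |
| 31 | 3 | 60 | 180 | 85 vs 64 | 43% |
| 31 | 3 | 90 | 180 | 127 vs 106 | 50% |
| 31 | 3 | 120 | 180 | 155 vs 127 | 51% |
| 31 | 6 | 90 | 180 | 127 vs 106 | 82% |
| 31 | 6 | 120 | 180 | 183 vs 127 | 83% |
| 18 | 2 | 90 | 150 | 127 vs 106 | 42% |
| 13 | 2 | 90 | 150 | 127 vs 106 | 47% |

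Over all follow-up assumptions for a cohort of 31, the median was longer in about 26 to 34% of trials with 2 such patients, 39 to 51% with 3 and 73 to 83% with 6. Otherwise it was equal; it was never shorter. With 1 of 18 or 1 of 13 the typical median stayed at 106 days. For a true median of 90 days, the event-free proportion at Day 127 was 0.42 against 0.38 with 2 of 31, and 0.50 against 0.38 with 6 of 31. Leaving the no-baseline patients out altogether gave the same median as Day 1 censoring in every trial.

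**The case against.** The strongest reply is that the case may never arise. The questionnaire heads the Cycle 1 Day 1 list in protocol Section 11 and should be completed before treatment. The one systematic cause of missing forms that protocol 12.3.4 names, lack of a suitable translation, would usually remove all of a patient's forms, and the rule already sends such patients to Day 1. The endpoint is also descriptive (SAP Section 8), and no test or go/no-go rule uses it. All of this stands. It limits the size and the consequence, but supplies no rule for a patient who misses only the first form.

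A reader might infer more than the documents support:

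- *That the reported medians will be too long.* This depends on at least one patient lacking a baseline and returning later forms. No rate is given.
- *That the bias is large.* In a very large sample with a fraction m unable to have an event, the curve tends to m + (1 − m)S(t). For an assumed true median of 84 days, the reported median is 84 × log2[(1 − m)/(0.5 − m)]: 91, 98 and 119 days at m = 5%, 10% and 20%. The arithmetic is right, but the 84 days and the fractions are assumptions. 20% of 31 is about 6 patients, and in small cohorts on a visit grid one or two such patients often leave the median unchanged.
- *That a baseline below 10 is the same defect.* Such a score cannot fall by 10 points, but it and the later scores are observed, and under the SAP definition the patient has no event. Censoring at Day 1 would discard observed data and change what is estimated. With ECOG 0 or 1 required at entry, such scores should also be rare.
- *That the rule will create a false difference between dose cohorts.* That needs unequal baseline completion, for which there is no evidence.

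**Conclusion.** The concern holds as a conditional one. The SAP states a rule that, when followed, keeps patients without a baseline score at risk for an event they cannot have. If there are any such patients, the Kaplan-Meier estimate is unchanged or too high, never too low; if there are none, there is no bias.

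Under the assumptions above, 2 of 31 such patients lengthen the reported median in about a quarter to a third of trials, and 3 of 31 in about 40 to 50%. With 2 of 18 or 2 of 13, the typical median moves by one 21-day visit interval, although in any single trial it is lengthened in somewhat fewer than half of cases. These figures rest on assumed event and follow-up rates and on a missing baseline being unrelated to outcome. This is a minor correction to a secondary, descriptive endpoint and affects no decision of the trial.

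**What to change.** Add to SAP 8.3.1: patients with no baseline global health score, or with no post-baseline global health score, are censored at the date of first study treatment (Day 1), and their number is reported for each expansion cohort. The post-baseline clause mostly restates what the rule already does; it adds the patients whose later forms yield no computable score. Do not extend the rule to patients with a low but observed baseline.

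SAP 1.2 allows the efficacy plan to be modified before database lock. The cost is one sentence and one derivation flag. The downside is that a few patients contribute no follow-up to this endpoint. If the reported number is zero, the reader can see that the median is unaffected.

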## 9. Safety Analyses

Summary of AEs and other safety parameters will be based on the SAS by treatment group as described in Section 6.1, except for the DLT, which will be based on DLT-Evaluable Set (DES) by treatment group.

### 9.1 Exposure

In the combination portion of the study, Cycle 1 through Cycle 6, doxorubicin will be administered at 75 mg/m^2 on Day 1 of each 21-day cycle. A maximum of six cycles of doxorubicin (18 weeks of treatment) is permitted.

In Cycle 1 through Cycle 6, PF-07901800 will be administered by intravenous infusion over 120 minutes on Day 1 and Day 8 of each 21-day cycle. Beginning with Cycle 7, PF-07901800 will be administered as monotherapy on Day 1 and Day 15 of 28-day cycles until documentation of disease progression or unacceptable toxicity. Monotherapy will be considered starting on the first cycle without doxorubicin.

PF-07901800 dose levels planned for evaluation in combination with doxorubicin in the dose escalation portion of the study are as follow:

Dose Level	PF-07901800 Dose
1	0.2 mg/kg
2	0.7 mg/kg
3	2.0 mg/kg

During the dose expansion portion of the study, two dose levels of PF-07901800 are planned to be evaluated in combination with fixed-dose

Pfizer Inc. / Protocol: TTI-621-03/C4961003  
IQVIA Biotech (Confidential) Project # YXA42460

doxorubicin. The low dose of PF-07901800 is anticipated to be 0.2 mg/kg and the high dose is anticipated to be the maximum of other PF-07901800 dose levels evaluated in the dose escalation portion of the study, prospectively planned to be 2.0 mg/kg, but alternate dose levels may require evaluation and a different dose may be taken forward based after discussion with treating physicians and the Sponsor.

Exposure to PF-07901800 and doxorubicin will be summarized with descriptive statistics for the number of non-zero doses received, duration of dosing (weeks), total cumulative dose (mg/kg for PF-07901800, mg/m^2 for doxorubicin).

Total cumulative dose is the sum of the actual doses of PF-07901800 or doxorubicin received.

Duration of dosing is defined as the time (in weeks) from first dose of study drug in cycle 1 to the last dose of study drug in the last cycle a patient had.

The calculation algorithm for duration of exposure (in days) for each drug will be:

- Doxorubicin:
  - o Last Doxorubicin dose date – first Doxorubicin dose date + 21
- PF-07901800:
  - o If the last dose is on Day 1 of Cycles 1-6: (Last PF-07901800 dose date – first PF-07901800 dose date + 7)
  - o If the last dose is on Day 8 of Cycles 1-6, and any time after Cycle 6: (Last PF-07901800 dose date – first PF-07901800 dose date + 14)

The number of participants with infusion interruption, dose reduction, infusion held (i.e. dose omitted) from study drug administration CRFs and number of participants with cycle delayed from date of visit CRF will also be summarized descriptively for each study drug by treatment group.

In addition, the planned dosing date and the actual dosing date will be listed. Listings will be provided with the information from all the study drug administration eCRFs. Reasons for missed doses, and reasons for dose reduction, infusion interruption, and cycle delay of PF-07901800 and Doxorubicin will be listed.

## 9.2 Dose-Limiting Toxicity

Pfizer Inc. / Protocol: TTI-621-03/C4961003  
IQVIA Biotech (Confidential) Project # YXA42460

Dose-limiting toxicity (DLT) is defined as a hematologic and/or non-hematologic treatment-emergent adverse event that occurs during the 21-day Cycle 1 and that are judged by the Investigator as related to PF-07901800 or the combination of PF-07901800 and doxorubicin, in those patients receiving the full dose of doxorubicin and the planned doses of PF-07901800 on Cycle 1 Day 1 and Day 8 and have been followed for the entire 21-day DLT period. Hematologic and Non-Hematologic AEs to be considered as DLT are listed in the study protocol. These DLT will be summarized, including number and percentage of patients, in the DES.

Adverse events that are in the opinion of the investigator attributable exclusively to intravenous infusion of doxorubicin or any doxorubicin prophylaxis medication will not be considered a dose-limiting toxicity. AEs and Serious AEs (SAE) will be determined to be dose-limiting if they occur in this timeframe and meet the described criteria. AEs or SAEs experienced after the end of Cycle 1 will not be reported as DLTs but will be documented. Patients who experience a DLT (other than grade 5) will remain on the study to complete the safety evaluations and follow-up until resolution or stabilization of the DLT.

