#### 5.4. Dose-Limiting Toxicity Criteria for the Dose Escalation Portion of the Study

Dose-limiting toxicity is defined as any of the following treatment-emergent adverse events that occurs during the 21-day Cycle 1 and that are judged by the Investigator as related to TTI-621 or the combination of TTI-621 and doxorubicin. Adverse events that are in the opinion of the Investigator attributable exclusively to intravenous infusion of doxorubicin or any doxorubicin prophylaxis medication will not be considered a dose-limiting toxicity.

CCI

CCI

Infusion-related reactions with TTI-621 are not unexpected and prophylaxis guidelines are provided in [Section 5.2.1.2](#) to mitigate their occurrence and/or severity. While the Investigator may decrease the duration of TTI-621 infusion and/or may decrease or eliminate the steroid component of TTI-621 prophylaxis in a patient who has not experienced infusion-related reaction, caution is urged with respect to implementing both changes simultaneously and a stepwise approach is recommended.

In the event that one patient in a cohort of three patients experiences a dose-limiting toxicity, the cohort will be expanded to a total of six patients. If at least two patients within a dose cohort experience a dose-limiting toxicity during the dose-limiting toxicity period, the conclusion may be drawn that the maximum tolerated dose of TTI-621 in combination with 75 mg/m^2 doxorubicin has been exceeded; any further dose escalation, de-escalation or cohort expansion will be decided in consultation between Investigators, the Sponsor Medical Monitor and the Sponsor after consideration of the particular patients and adverse events experienced, as well as all available safety and pharmacokinetic data of all cohorts.

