$50 \times 10^9 – 25 \times 10^9/L$	
 
Omit TTI-621 on Day 8
 
Monitor platelet recovery (CBC twice weekly recommended)
 
Consider platelet transfusion per ASCO guidelines if clinically indicated
 
On Day 1 of next cycle: 
 
if platelets have recovered to <math>\geq 75 \times 10^9/L</math>, initiate cycle with doxorubicin at the same dose and TTI-621 at one dose level reduction
 
if platelets have not recovered to <math>\geq 75 \times 10^9/L</math>, hold doxorubicin and TTI-621 and monitor platelets; initiate the cycle when platelets recover to <math>\geq 75 \times 10^9/L</math> with doxorubicin at same dose and TTI-621 at one dose level reduction
 
 
 
In the case of a second occurrence of platelet count decrease to <math><50 \times 10^9</math>, follow the guidelines above or consult with the Sponsor Medical Monitor regarding management
 
The reduced dose of TTI-621 should be used for the remaining combination cycles
 
When the subject completes the combination portion of the study and moves to TTI-621 monotherapy: 
 
the original TTI-621 dose level should be re-instated and platelet counts monitored
 
in the case of platelets <math>< 50 \times 10^9/L</math> without other causality on Day 15, hold TTI-621 until platelets are <math>\geq 50 \times 10^9/L</math> and then continue with TTI-621 at a one dose level reduction
 
on second occurrence of platelets <math>< 50 \times 10^9/L</math> without other causality, reduce TTI-621 by an additional dose level and monitor for tolerability or consult with the sponsor medical monitor regarding management
 
in the absence of disease progression, further dose reductions may be implemented after discussion with the sponsor medical monitor
 
 
 

Platelet Count on Day 8	Management Guidelines

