### 12.2. Analysis Populations

The following analysis populations are defined for the study:

**Safety population:** all patients who received at least 1 dose of TTI-621

**Efficacy population:** all patients who received at least 1 dose of TTI-621

**DLT-evaluable population:** all patients who received the full dose of doxorubicin and the planned doses of TTI-621 on Day 1 and Day 8 and have been followed for the entire 21-day DLT period (i.e., Cycle 1) or who have a DLT during Cycle 1 will be considered DLT-evaluable

**Response-evaluation population for Simon two-stage design:** all patients in either Expansion Cohort A (low dose TTI-621) or Expansion Cohort B (high dose TTI-621) who complete at least two cycles of treatment as described in the protocol and have a post-treatment objective disease assessment unless they were withdrawn prior to meeting this criterion for safety or earlier demonstration of objective disease progression

**CCI** [REDACTED]: all patients who received at least one dose of TTI-621 and have at least one evaluable blood sample for analysis collected

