### 6.7.3 DLT-Evaluable Set (DES)

The DES is applicable to dose-escalation cohorts only. It will include patients who received the full dose of doxorubicin in Cycle 1 Day 1 and the planned doses of PF-07901800 on Day 1 and Day 8, and

Pfizer Inc. / Protocol: TTI-621-03/C4961003  
IQVIA Biotech (Confidential) Project # YXA42460

have been followed for the entire 21-day DLT period (Cycle 1) or who have a DLT during Cycle 1.

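### SAP 9.2 makes full Day 1 and Day 8 dosing and complete 21-day follow-up part of the DLT definition, so read literally the DLT summaries omit a Cycle 1 DLT that prevents either

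*SAP*

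**What the plan says.** SAP 9.2 defines a DLT by type of event, Cycle 1 timing and attribution, and then adds two conditions on the patient. The first concerns dosing: the event must occur "in those patients receiving the full dose of doxorubicin and the planned doses of PF-07901800 on Cycle 1 Day 1 and Day 8". The second, joined to the first with no alternative offered, concerns observation; these patients must also meet the requirement "and have been followed for the entire 21-day DLT period". It goes on to say that "Hematologic and Non-Hematologic AEs to be considered as DLT are listed in the study protocol", and that the number and percentage of patients with a DLT will be summarized in the DLT-evaluable set (DES). Its second paragraph states: "Patients who experience a DLT (other than grade 5) will remain on the study to complete the safety evaluations". SAP 9.3 adds a DLT table by SOC and PT.

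The other definitions differ:

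- Protocol 5.4: "Dose-limiting toxicity is defined as any of the following treatment-emergent adverse events that occurs during the 21-day Cycle 1", with attribution to TTI-621 or to the combination. The visible text sets no dosing or follow-up condition. The list of qualifying events is redacted.
- SAP 6.7.3 (DES): patients with the required dosing who "have been followed for the entire 21-day DLT period (Cycle 1) or who have a DLT during Cycle 1".
- Protocol 12.2: completers of dosing and follow-up, "or who have a DLT during Cycle 1 will be considered DLT-evaluable".
- Protocol Synopsis (Study Design) and Section 5.1: a patient is evaluable for DLT if given doxorubicin on Day 1 and TTI-621 on Days 1 and 8 of Cycle 1. This sentence has no alternative for a patient with a DLT. The replacement rule that follows it does not replace a patient who withdraws in Cycle 1 with a DLT.

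**The concern.** Dosing and follow-up conditions normally decide who belongs in the denominator when no DLT has been seen. SAP 9.2 moves them into the definition of the event. A toxicity severe enough to cancel the Day 8 dose, or to kill the patient before Day 21, then fails the definition because of its own consequences. These are the DLTs that a reader of the table most needs to see, and the error can run in only one direction, towards a lower reported rate.

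Toxicity that cancels Day 8 is foreseen. Protocol 9.5, Table 22, covering Cycles 1 to 6, says "Omit TTI-621 on Day 8" for Day 8 platelets between 50 and 25 x 10^9/L, and again for counts below 25 x 10^9/L. Whether such an event is a DLT cannot be checked, because the criteria in Protocol 5.4 are redacted.

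At stake is the reported DLT summary, which describes the escalation phase and accompanies the primary objective of establishing the maximum tolerated dose.

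**Working it through.** **1. The passages side by side.** Take a patient who has a qualifying, attributable event in Cycle 1 and, because of it, misses the Day 8 dose.

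- Protocol 5.4, visible text: the event is a DLT.
- Protocol 12.2: the patient is evaluable through the DLT alternative.
- SAP 6.7.3: the patient is in the DES through the same alternative.
- SAP 9.2: the event is not a DLT, because the Day 8 dose was not given.

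If 9.2 supplies the meaning of DLT, the DLT alternative in SAP 6.7.3 can add nobody: only a patient who already meets the dosing and follow-up conditions could have a DLT. The two SAP sections cannot both operate as written. SAP 9.2 also provides for a grade 5 DLT, yet a patient who dies before Day 21 cannot have been followed for 21 days.

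**2. The plan's own figure.** The Protocol (Synopsis and 12.1.1) and SAP 4.3.1 give 9 to 18 patients for escalation. Three dose levels with 3 or 6 patients each give 3 x 3 = 9 and 3 x 6 = 18, which reproduces the range.

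**3. Effect on the reported rate.** Let N be the patients in a column under SAP 6.7.3, d the Cycle 1 DLTs, and e those DLTs that stopped the Day 8 dose or the 21-day follow-up.

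- Protocol 5.4 with SAP 6.7.3: d/N.
- Literal 9.2, with those patients also leaving the DES: (d - e)/(N - e).
- Literal 9.2, with those patients kept in the denominator: (d - e)/N.

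Because d is at most N, neither literal version can exceed d/N. The documents give no DLT counts, so d and e below are assumed. They are limited to at most one DLT per six-patient cohort, the rule for a level deemed safe.

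| Assumed case | d/N | (d - e)/(N - e) | (d - e)/N |
|---|---|---|---|
| One cohort of 6; d = 1, e = 1 | 1/6 = 16.7% | 0/5 = 0% | 0/6 = 0% |
| Phase 1 total 3+3+6 = 12; d = 1, e = 1 | 1/12 = 8.3% | 0/11 = 0% | 0/12 = 0% |
| Phase 1 total 6+6+6 = 18; d = 3, e = 1 | 3/18 = 16.7% | 2/17 = 11.8% | 2/18 = 11.1% |
| Any N and d; e = 0 | d/N | d/N | d/N |

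The third row uses three DLTs because under the 3+3 rule a cohort normally grows to six after a DLT. Three cohorts of six therefore normally imply at least three.

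**The case against.** The best defence is that the clause is loose shorthand for the DES. SAP 9.2 summarizes DLTs in the DES, and the DES expressly keeps patients with a Cycle 1 DLT. A later sentence of 9.2 classifies an event by timing and the described criteria without repeating the dosing condition. The mention of grade 5 also shows that early fatal DLTs were meant to count. As a statement of intent this is plausible, and a careful programmer might well produce the right table. It does not remove the point. The condition stands explicitly in the definition that specifies this output, the described criteria may be read to include it, and the sentence deferring to the protocol covers only which events qualify. The correct result should not depend on ignoring part of a definition.

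The objection about consequence stands. Escalation follows the protocol rules and the review by sponsor and investigators (Synopsis, 5.1, 5.4), not the SAP table. The events remain in the other TEAE tables, including TEAEs leading to drug interruption (SAP 9.3), in the listed reasons for missed doses (SAP 9.1) and, if fatal, in the death outputs (SAP 9.4). The listing of all DLTs in SAP 9.3 is not restricted to the DES, but it relies on the same term.

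A reader might infer that the Grade 3 or 4 thrombocytopenia on Day 8 in Cohort B (SAP 4.3.2) would be lost from the DLT table. The documents do not support this: the DES covers escalation cohorts only, so Cohort B patients never enter that table. A reader might also infer that 9.2 is the only text out of line. The evaluability sentences in the Protocol Synopsis and Section 5.1 also lack the DLT alternative.

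**Conclusion.** The inconsistency is real and minor. SAP 9.2, as written, excludes a Cycle 1 DLT that prevents Day 8 dosing or 21-day follow-up, contrary to the visible Protocol 5.4, Protocol 12.2, SAP 6.7.3 and its own reference to grade 5. Followed literally, it can lower the reported DLT rate or leave it unchanged, never raise it. In the assumed cases the reported figure falls from 16.7% to 0% in one six-patient cohort, from 8.3% to 0% in a 12-patient total, and from 16.7% to 11.8% or 11.1% in an 18-patient total.

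This rests on two unknowns: whether any DLT interrupted dosing or follow-up, and whether the programming would follow the clause. If either answer is no, nothing changes. It would go too far to infer that dose selection or the maximum tolerated dose is compromised, since the protocol's escalation decisions do not use this table. Nor do the documents show that any DLT was in fact omitted.

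**What to change.** In SAP 9.2, delete the clause that restricts DLTs to patients with full dosing and complete 21-day follow-up. Define a DLT by reference to Protocol 5.4 and summarize it in the DES of SAP 6.7.3, so that every Cycle 1 DLT in the escalation cohorts is counted whether or not Day 8 was given or follow-up completed. Align the evaluability sentences in the Protocol Synopsis (Study Design) and Section 5.1 with Protocol 12.2 by adding the alternative for patients with a DLT.

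The cost is one deleted clause in the SAP and matching wording in two places in the protocol. No new data, tables or analyses are needed, and the reported DLT percentage stays the same or rises.
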